#### Intervention group

The researcher or the research assistant will collect the fluid chart given previously and clarify with the patient regarding their entries on the fluid chart. After the patient's consultation with their respective doctors, the researcher or the assistant will give a new fluid chart to the patient if they had been given a another clinic appointment for outpatient monitoring.

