- b) Healthcare provider administering the tool
- c) Patient understanding and adherence to the tool

The literature review, designing and developing the fluid chart and planning for this pilot study was all part of the theory and modelling process. This was followed by the pilot study which is an exploratory trial in Phase II of the MRC framework. This exploratory trial tests out the experimental intervention and the process of evaluation. This pilot study also generates and determines the trend of the preliminary results crucial to calculate the sample size for the definitive randomised controlled trial.

The first point of medical care for febrile patients living in any community at large will usually be the primary healthcare centres. In addition to this, patients tend to consult the primary healthcare providers early when they have fever. However, the clinical features of early dengue fever are very similar to that of other febrile illnesses, making the distinction between the two fraught with difficulties. Many studies have attempted to identify differentiating clinical and laboratory features between dengue and other febrile illnesses. Some studies have proposed the usage of decision tree algorithms and diagnostic models to aid primary care clinicians to identify probable dengue cases early. However, none of these diagnostic models or decision algorithms have been validated or widely used in other countries.

Another added barrier to early diagnosis of dengue fever is that to confirm a case of acute dengue infection, the serologic test results are only obtained after several days up to one week. This is because detection of newly formed antibodies (IgM) would not be possible until after viraemia ends or after fever subsides. The first detectable dengue IgM begins to appear on day 4 to day 5 of illness. Expensive laboratory tests yielding faster results are usually not available in resource-poor countries.

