#### Method of intervention received by the control group only

Apart from this, the control group will be asked their twenty four hour fluid recall. This means that the patient will be asked to give an estimate of how much fluid they have drunk in the twenty four hours prior to the current consultation with the researcher or the trained research assistants.

This estimate will be given by the patients in terms of how many litres or millilitres of fluid they drank, how many glasses (small or large sized glasses or mugs), or how many bottles of drinks they had (500ml size, 1 litre size, or 1.5 litre size), or how many packet drinks they had. Details on what type of fluids is consumed orally will be obtained. This information will be obtained during recruitment of the patient, and on each subsequent follow-up.

One should take note that no fluid chart or cup will be given to the control group participants.

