## Method of intervention received by the intervention group

The patients assigned to the intervention group will be given a plastic cup of uniform size, along with a twenty four hour fluid chart. These patients will be instructed to use the cup for drinking any form of fluid they wish to consume for the duration of their participation in the study. Verbal instructions will be given on how to fill in the various details required on the fluid chart regarding their oral fluid consumption.

This will be done over the next twenty four hours or until they come for their next follow-up consultation at the clinic. If the next clinic follow-up will be given at the interval of a few days after the preceding consultation, then the researcher or the trained research assistant will provide enough fluid chart forms for the patient to fill until the next consultation.

The patient will be instructed to write down the amount of fluids they drank according to the time that they consumed the fluids in the second column. The patients will be instructed to record the type of fluids they drink in the third column. The patient will only fill the last column if they received any intravenous fluid drip over the next twenty four hours. They are to record the amount of bottles of fluid they receive intravenously.

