## **Control group**

The researcher or the research assistant will obtain data regarding the twenty four hour fluid recall and the types of fluids consumed for each subsequent follow-up visit.

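### No intake measure is stated for an intervention patient who attends without a usable fluid chart, so the oral intake comparison risks adherence-related missing data in one arm only

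*Protocol*

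**What the plan says.** **Control arm.** Under the heading for the control group only: "Apart from this, the control group will be asked their twenty four hour fluid recall". On timing: "This information will be obtained during recruitment of the patient, and on each subsequent follow-up". The Follow-up section repeats that the researcher or assistant "will obtain data regarding the twenty four hour fluid recall and the types of fluids consumed for each subsequent follow-up visit". The patient needs to bring nothing.

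**Intervention arm.** Patients receive a uniform cup and a 24-hour chart, with enough forms to last until the next visit. "The patient will be instructed to write down the amount of fluids they drank according to the time that they consumed the fluids" (Method of intervention received by the intervention group). At follow-up, staff "will collect the fluid chart given previously and clarify with the patient regarding their entries on the fluid chart".

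**Both arms.** The follow-up items listed for both groups are blood results, serology if taken, and temperature. Intake is not among them. Item 5 of Preliminary outcome measures then compares the amount of oral intake between the groups.

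**Adherence.** The Background lists "Patient understanding and adherence to the tool" as one of the three interacting components of the intervention.

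**The concern.** A control contributes a follow-up intake value by attending. An intervention patient contributes one, as far as the text goes, by attending and also having kept and brought back a chart with entries. The second condition is adherence to the assigned intervention. Values that go missing for that reason go missing in one arm only. If patients who keep charts differ in intake from those who do not, the groups compared are no longer those that randomisation formed. This would hold even if chart and recall were equally accurate, so it is separate from the question of whether the two instruments measure alike.

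The stake is the intake effect estimate. The Study objectives use the pilot's preliminary results to estimate the treatment effect and to calculate the main trial's sample size. An overstated intake effect would make a trial sized on it too small; an understated one would do the reverse.

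**Working it through.** **1. Is there another route to an intake value in the intervention arm?** The places where one could stand:

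- Method of intervention, control group only: recall at recruitment and each follow-up, controls only.
- Method of intervention, intervention group: chart and cup; no recall.
- Follow-up, Intervention group: collect the chart and clarify its entries. This presupposes a chart with entries.
- Follow-up, Both groups: no intake item.
- Defaulter tracing: reason for non-attendance, a new visit, admission details; no intake question.
- Defaulted follow-up and drop out: defined by visits, so a patient who attends without a chart is neither.
- Conversions used for calculation of total fluid intake: container volumes; no rule for a blank or partial chart.

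No visible passage supplies a value for the attending patient with a missing or blank chart. The recruitment recall is also described for controls only, so the text offers no baseline intake from which to impute.

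**2. The plan's own figure.** The minimum is 30 per group, 2 × 30 = 60 (Estimated sample size). No effect size, SD or power is attached, so nothing further can be reproduced.

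**3. Illustration in SD units.** The document gives no chart return rate and no link between charting and intake, so both are assumed.

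- Attending patients per arm, using the 16.4% default rate of the prior study at the same clinic as a rough guide: 30 × (1 − 0.164) = 25.08, about 25.
- r = share of attending intervention patients with a usable chart. ρ = correlation between intake and the tendency to return a chart.
- Bias if patients without a chart drop out of the comparison: ρ × φ(z) / r, where z is the (1 − r) quantile of the standard normal and φ its density.
- Example, r = 0.8: z = −0.842, φ = 0.280, 0.280 / 0.8 = 0.350. With ρ = 0.3 the bias is 0.105 SD; with ρ = 0.5 it is 0.175 SD.

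Rejection rates come from 20,000 simulated Student's t tests per setting, 25 controls against 25 × r charts (rounded down), no true effect, two-sided 5% level (sidedness is not stated in the Protocol).

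| r | charts | bias, ρ = 0.3 | bias, ρ = 0.5 | rejection, ρ = 0.3 | rejection, ρ = 0.5 |
|---|---|---|---|---|---|
| 1.0 | 25 | 0 | 0 | 5.0% | 5.0% |
| 0.9 | 22 | 0.058 | 0.097 | 5.5% | 6.0% |
| 0.8 | 20 | 0.105 | 0.175 | 6.6% | 8.7% |
| 0.6 | 15 | 0.193 | 0.322 | 8.5% | 16.1% |
| 0.5 | 12 | 0.239 | 0.399 | 10.2% | 19.8% |

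With ρ = 0 there is no bias at any r, and rejection stays near 5%. A negative ρ reverses the sign.

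**4. Why the direction is open.** Dropping patients without charts shifts the arm mean by (1 − adherence) × (intake gap between those who chart and those who do not). With assumed adherence of 90% to 60% and a gap of 300 to 600 ml/day in favour of those who chart, this is (1 − 0.9) × 300 = 30 to (1 − 0.6) × 600 = 240 ml/day too high. If instead 20% of drinks at a true 2,000 ml/day go unlogged, are not recovered by clarification and count as nothing, the arm is 0.20 × 2,000 = 400 ml/day too low. All these inputs are assumptions.

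**The case against.** A reader might infer that item 5 compares chart adherers with all controls. The document does not support that. It nowhere says that patients without a chart are excluded or that gaps are summed as zero, and how missing records are counted may stand in an analysis plan that is not shown. Controls who never return give no follow-up recall either, so the comparator is attending controls.

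Further points carry weight. Staff go through the entries face to face, which is a natural way to complete a partly filled chart. The flow diagram and the data collection form cited under Data collection are not available here, and the form may hold an intake field for both arms. Control intake is not error-free: the Background itself says recall is open to recall bias.

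A reader might also infer that poor adherence would be hidden inside the intake result. It would not be. Chart usage is an explicit feasibility and acceptability objective, and charts are physically collected, so non-return would be seen.

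What remains is narrower. Clarification does not help when there is no chart or no entry, and an analysis plan can set a rule for missing values but cannot supply intake that nobody asked about.

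**Conclusion.** The point holds as a gap in data collection. As written, the patient-completed chart is the only follow-up intake source in the intervention arm, while each attending control gives a recall taken by staff. Item 5 therefore risks missing data in one arm only, related to adherence to the assigned tool.

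Neither size nor direction can be derived from the document. The figures above show that the effect ranges from nil (full return, or return unrelated to intake) to 0.399 SD at 50% return with ρ = 0.5. They rest on assumed return rates and correlations and on patients without charts dropping out of the comparison, which is inferred from the lack of a fallback. The statement that the planned comparison is one of adherers against all controls goes further than the text.

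Item 5 is one of several preliminary outcomes in a time-driven pilot, so this is a modest fault. It is worth correcting because the correction is cheap and must be in place while patients are being seen.

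**What to change.** - At each follow-up visit, take the same 24-hour recall from intervention patients as from controls. At minimum, take it whenever the chart is missing, blank or cannot be completed by clarification. Record the source of each value.
- Compare item 5 in all randomised patients who attend, whatever their chart use, on the common recall where it is taken in both arms. Do not count an incomplete chart as a full day.
- Report chart return and completeness separately, under the existing feasibility and acceptability objective.

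Cost: a few minutes per visit and a few form fields. Some intervention values then come from recall, with its error. The minimum version also mixes instruments within one arm according to adherence, which is why recall in both arms at every visit is preferable. The Aim sets the chart against 24-hour recall, so if recall is taken in both arms the text should say that it serves as a measurement and that the chart and cup are what differs. The comparison remains conditional on attendance.

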## Both groups

The following data will be recorded on the data collection form for each subsequent clinic follow-up visit: Their blood investigations, namely their haemoglobin, haematocrit levels, total white cell count, platelets, if dengue serology had been taken, as well as their temperature readings. The participants' management will be handled by their respective doctors. Thus, it is at their discretion whether or not to do a dengue serology test, and the timing of the test. Generally a full blood count test will be ordered for each subsequent clinic visits for outpatient monitoring

Some of the patients have to pay for their own blood test if they were not in government service. However, should the dengue serology results yield a positive IgM result, then the patients can claim the money they had spent for the blood tests. This reimbursement is borne by the Malaysian Government.

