# Follow-up

## Duration

All the patients recruited into the study will be followed up until they are clinically better and/or their laboratory markers show improvement as assessed by the respective doctors. Thus, different patients will be followed-up for different lengths of time.

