## **Blood tests**

## Method

The full blood count test will be done using the Sysmex XT-1800 and Sysmex XT-2000 machine at the laboratory situated on the ground floor of the clinic. The platelet count will be measured using the hydrodynamic focusing (DC) detection mechanism, whereas the haematocrit level will be calculated via the red blood cell (RBC) pulse height detection method. Both of these methods will be performed by the Sysmex XT machine.

The dengue serology test will be performed using the Standard Diagnostics Dengue IgM capture ELISA, which is done at the medical virology laboratory in the main situated in the main hospital building. The mean sensitivity of this test is 97.6%, with a 95% confidence interval of 96.8%-98.4%. The mean specificity of this test is also high, which is 90.0%, with a 95% confidence interval of 88%-91.7%.

However, no confirmatory tests will be done such as PCR as such tests are very expensive, unavailable in the normal primary healthcare setting, and would not have an impact in the management of these patients. The IgG titres will not done for the participants in this study, even though many of whom have a paired sera sample. This was because this was not the standard practice for the laboratory handling the dengue serology specimens from the primary healthcare clinic.

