## Tracing

Either the researcher or the trained research assistants will trace the full blood count daily using the online computer system for patient recruitment or follow-up purposes. The results of the dengue serology test will be traced one week after the date of testing. All the information obtained will be recorded on the data collection sheet.

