## Defaulter tracing

For those who does not turn up for the follow-up with the researcher or the trained research assistants, an attempt will be made to contact the patient via the telephone, with a maximum of three attempts. During the telephone consultation, either the researcher or the trained assistant will attempt to find out the reason why the patient did not come for the follow-up appointment that was given. The patient will then be asked whether they will be amenable to come for follow-up the next day or at the next nearest date when convenient.

If the patient did not come for follow-up as he or she has been admitted to hospital, then details regarding the admission will be obtained. Such details will include which hospital they have been they admitted to, the date of admission, the reason for the admission and who recommended for the admission i.e. was it by medical personnel or did the patient themselves request for the admission. All these details would be entered on the standardized data collection form.

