## Preliminary outcome measures

The outcomes will be assessed at the end of the two month period of data collection.

Several preliminary outcomes measures will be used to assess the trend of the preliminary results in order to determine the treatment effect size of the fluid chart. The two pilot study groups will be compared in terms of:

- 1. The hospitalization rates
- 2. The need for intravenous fluid treatment
- 3. The severity of haemoconcentration. Four surrogate endpoints were utilized to determine this, and they were as follows:
  - a. The mean peak haematocrit
  - b. The difference in haematocrit level between the values of clinic consultation 2 clinic consultation 1.
  - c. Those above the local cut off value of haematocrit indicative of plasma leakage.
  - d. Haematocrit fluctuation of 20% or more
- 4. With regards to assessing the severity of the platelet drop, two secondary endpoints were used:
  - a. The mean nadir platelet count
  - b. The difference in the platelet level between the values of clinic consultation 2 clinic consultation1.
- 5. The difference in the amount of oral fluid intake between the two groups.

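### Blood counts after admission are not secured, so the peak and nadir endpoints can be cut short by hospitalisation, which is itself an outcome

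*Protocol*

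**What the plan says.** Haematocrit and platelets belong to the visit record: "The following data will be recorded on the data collection form for each subsequent clinic follow-up visit" (Protocol, Follow-up, Both groups). The same section describes testing as usual practice, not as a schedule: "Generally a full blood count test will be ordered for each subsequent clinic visits for outpatient monitoring". Full blood counts are run "at the laboratory situated on the ground floor of the clinic" (Blood tests, Method).

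Under Duration, patients are followed until the doctor judges them clinically better or improved on laboratory markers, so "different patients will be followed-up for different lengths of time".

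When a patient misses follow-up because of admission, the team obtains details by telephone: "Such details will include which hospital they have been they admitted to, the date of admission, the reason for the admission", and who recommended it (Defaulter tracing). No blood values are listed. Under Tracing, the team "will trace the full blood count daily using the online computer system for patient recruitment or follow-up purposes". Inpatient results are not mentioned.

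Preliminary outcome measures puts hospitalisation first. It also lists mean peak haematocrit, a 20% haematocrit fluctuation (defined later from the highest haematocrit), exceeding a local haematocrit cut-off, "The mean nadir platelet count", and the changes from consultation 1 to consultation 2. Background states that haematocrit and platelets, together with the clinical condition, inform the decision to admit.

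**The concern.** Peak, nadir, the 20% endpoint and in effect the cut-off endpoint all depend on the most extreme value recorded. If recording ends at admission, and admission is triggered partly by the value being recorded, the series stops early in the patients who are worsening. This truncation is informative, and the event that causes it may be affected by the intervention.

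An arm that avoids admissions keeps more of its sicker patients under clinic observation, so more of their worst values are recorded. The other arm's worst values are more often missing. The hospitalisation result and the severity result could then point in opposite directions for reasons of data capture alone.

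This matters even in a pilot, because Study objectives (item 3) uses these trends to estimate the effect size and to size the main trial. A statistical analysis plan could not repair it later if the values were never collected.

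**Working it through.** The plan gives no figure to reproduce. The minimum of 30 per group comes without an effect size, SD or power. What follows is illustrative.

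**Inputs from the protocol**
- At least 30 per group (Estimated sample size); significance at p < 0.05, taken here as two-sided (Statistical analysis).
- Admission among suspected cases in the three preceding months: 55.4%, 40% and 63.41% (Study setting). Simple mean: (55.4 + 40 + 63.41)/3 = 52.9%. Patients found to need admission at the first visit are excluded, so the rate after enrolment may be lower.

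**Assumed inputs**
- Admission gap between arms: 20 points (10 points as a smaller case).
- d, the mean shortfall in SD units among admitted patients between the peak over a complete window and the highest recorded value: 0.25, 0.5 or 1.0. For a maximum, d cannot be negative. It is zero if haematocrit does not exceed the last recorded peak after admission.

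**Bias with no true difference, recorded intervention minus control**

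Bias = h_control × d_control − h_intervention × d_intervention, where h is the proportion admitted. If d is the same in both arms this is (h_control − h_intervention) × d. A positive value makes the intervention look worse on haematocrit; platelets are the mirror image. The rejection probability is Φ(b/√(2/30) − 1.96) + Φ(−b/√(2/30) − 1.96), where b is the bias.

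| Admission, control vs intervention | d (SD) | Control understated | Intervention understated | Bias (SD) | Rejection probability |
|---|---|---|---|---|---|
| 52.9% vs 32.9% | 0.25 | 0.13 | 0.08 | 0.05 | 5.4% |
| 52.9% vs 32.9% | 0.5 | 0.26 | 0.16 | 0.10 | 6.7% |
| 52.9% vs 32.9% | 1.0 | 0.53 | 0.33 | 0.20 | 12.1% |
| 20% vs 10% | 1.0 | 0.20 | 0.10 | 0.10 | 6.7% |
| 40% vs 40% | any, equal | equal | equal | 0 | 5% |

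Only the gap matters when d is equal: 40% vs 20% and 63.4% vs 43.4% give the same bias as 52.9% vs 32.9%. On the haematocrit scale, an assumed shortfall of 0.02 to 0.04 and a gap of 10 to 20 points give 0.10 × 0.02 = 0.002 to 0.20 × 0.04 = 0.008.

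The direction is not guaranteed. If d is 0.25 in control and 0.5 in intervention, the bias is 0.529 × 0.25 − 0.329 × 0.5 = 0.132 − 0.165 = −0.03 SD, which favours the intervention.

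**Simulation**

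Daily values rise and fall over five days, and admission occurs when a value crosses a threshold. The value that triggers admission is kept and recording then stops. The SD of the true peak is about 1.34 and no effect of intravenous fluid is modelled.

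| Scenario | Admission, control vs intervention | True difference | Recorded difference |
|---|---|---|---|
| Lower severity, same threshold | 53% vs 40% | −0.399 | −0.271 |
| Lower severity, higher threshold in intervention arm | 53% vs 27% | −0.395 | −0.175 |
| No effect, higher threshold in intervention arm | 53% vs 38% | −0.005 | +0.132 |

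If the main trial were sized on such an endpoint, the required number would be inflated by (0.399/0.271)² = 2.2 in the first scenario and (0.395/0.175)² = 5.1 in the second.

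**The case against.** A reader might infer that the worst values of all admitted patients are lost. The documents do not support that.
- The Tracing section has staff check full blood counts online every day and record what they find, and the clinic stands in the grounds of the hospital. Counts from a same-institution admission may well be picked up.
- The admission details under Defaulter tracing are introduced as included items, not as a closed list, and the data collection form is not shown.
- A patient admitted from a clinic visit keeps that visit's count, so someone admitted at consultation 2 would generally have the consultation 2 minus 1 change.

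These points limit the claim but do not answer it. No section commits to inpatient counts. Defaulter tracing asks which hospital, so admissions elsewhere are expected. The protocol also has to assume that admitted patients received intravenous fluid (Intravenous fluid drip), which suggests that inpatient records are not routinely reviewed. Capture in one hospital only would be uneven.

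A reader might also infer that follow-up stops on 30 July for late recruits. Time frame of data collection and Preliminary outcome measures point that way, but Duration follows every patient until improvement. The sections are unreconciled; they do not state a cut-off.

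On size, the assumed intravenous fluid may prevent any further rise in haematocrit, leaving little or no shortfall. Differing visit numbers add little by themselves. With an assumed independent visit-to-visit SD of 0.015, four visits instead of two raise the expected maximum by (1.029 − 0.564) × 0.015 = 0.007, but only if whole arms differ by two visits. If 10% to 20% of an arm differs, the shift is 0.0007 to 0.0014.

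Finally, this is a pilot whose main aims are feasibility and acceptability, and the protocol openly says that follow-up length varies. That lowers the urgency without removing the flaw.

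**Conclusion.** The point holds as a gap in data capture. Recording is tied to clinic visits of doctor-determined number, counts after admission are not secured, and admission is both an outcome and informed by the values measured. The four extreme-value endpoints can be truncated informatively, and the consultation 2 minus 1 changes are missing for patients admitted between those visits.

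Between-arm bias needs a difference in admission rates or in later worsening. Its most plausible direction is against the arm with fewer admissions. Under the assumptions shown it is 0.05 to 0.20 SD for a 20-point gap. That is small beside the difference 30 per group can detect with 80% power, (1.96 + 0.84) × √(2/30) = 0.72 SD. The main harm is therefore to the effect estimate carried into the main trial, not to the pilot's p values. With equal admission and equal later worsening, both means are understated but there is no between-arm bias under no true effect. The documents give neither the admission gap nor the change after admission, so they establish neither the size nor the direction. The change is worth making before recruitment, but the flaw does not undermine the feasibility aims.

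**What to change.** In Both groups, Tracing and Preliminary outcome measures:
1. Define the peak, nadir, 20% and cut-off endpoints over one fixed window from recruitment, the same for every participant (for example 7 days).
2. State that full blood counts in the hospital's online system are traced through that window whether or not the patient is admitted. Use at most one prespecified value per day, because admitted patients may be tested more often and unlimited counts could reverse the bias.
3. For admissions elsewhere, request haematocrit and platelet values in the telephone contact already planned.
4. Add a sensitivity analysis that ranks admitted patients without values as worst.
5. Reconcile Time frame of data collection and Preliminary outcome measures with Duration, so that tracing of late recruits completes the window.

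The cost is more look-ups in a system already checked daily and, with a 7-day window, about one more week of tracing. No extra blood tests are needed. Two limits remain. One value per day reduces unequal testing frequency but does not remove it. Some inpatient haematocrits will have been taken after intravenous fluid, which should be noted when they are interpreted.
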